Schools within the Tamale District with the highest rates of female student dropouts at the middle school level (based on retrospective 3-year data) will be compiled. Once the list is compiled, the ten schools with the highest female student dropout rates will be selected. Subsequently, schools will be randomly assigned to either control or treatment arm. Following school randomization, the study team will work closely with the schools for recruitment.

Participants

One hundred adolescent girls and their caregivers will participate in the study (n=50 dyads in each arm; 10 per school). Adolescent girls' inclusion criteria are: 1) Enrolled in school and living within a family (defined broadly -not necessarily biological parents); 2) Ages 11 to 14; 3) Capable of giving assent; 4) Skipping school in the past academic term (with at least 10% of unexcused absences). The caregiver inclusion criteria are: 1) Self-identified as primary caregiver of the adolescent girl; and 2) Capable of providing informed consent. Participants (girls and

caregivers) that do not meet the criteria or exhibit a lack of understanding of the study procedures and hence not able to provide informed consent will be excluded.

Recruitment, retention and attrition

School administrators will share a flyer that introduces the project to the students and caregivers; and invite all the caregivers with an eligible child/ren to contact the school for details. The study team will organize meetings with families in each of the selected schools to present the study and answer questions. The research team will then meet with potential participants to engage them in the screening and informed consent process. Adolescent girls will be contacted for assent only after receiving consent from their caregivers. Only families who provide both consent and assent will be recruited to participate in the study.

Study arms

Control arm (Bolstered care). Female adolescents in the bolstered care will receive services/education as usual in their respective schools. The usual care will be bolstered by providing school notebooks and lunch in the control arm (bolstered care will also be provided to treatment arm). Primary school education is universal and free in Ghana. Yet notebooks and lunch are costly expenses for families that create a barrier to school attendance. Hence, these will be provided to participants in all study schools.

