Psychosocial well-being (A)	1)Tennessee Self-Concept Scale Short Form 2)Rosenberg Self-Esteem Scale 3)Emotional Self-Efficacy Scale 4)Social Self-Efficacy Scale 5) Multidimensional Student Life Satisfaction Scale 6) Adolescent Stress Questionnaire
Family/social support (A, C)	1)Social Support Behavior Scale 2)Multidimensional Scale of Perceived Social Support
Family Relations (A, C)	1) Family Environment Scale (FES) 2) Family Assessment Measures (FAM)
Migration (A, C)	How likely they are to see themselves migrate? How like they are to send their daughters to work? Follow-up (6 months) are girls working?
Gender Attitudes (A, C)	1) Attitudes towards Women 2) Gender Norm Attitudes Scale
Future Orientation (A)	Thinking about the future
Feasibility	Recruitment rates; staff level of effort; number of screenings conducted; proportion eligible and agreed to enroll**; number of rescheduled, cancelled, missed sessions/ assessments to inform staffing needs and retention protocols for subsequent trial
Acceptability (A, C)	Client satisfaction Questionnaire (CSQ-8; to be adapted) Semi-structured interviews

A= adolescent, C= caregiver, B= bank

**Enrollment of 70% or higher will be considered feasible⁷¹

Measures that have been used in SSA are in italics

Measures that have been used in Ghana are in bold

The complete assessment battery is administered at each timepoint to inform future R01 level study, should findings warrant. The battery takes into account: 1) participant's literacy (read aloud procedures); 2) need for trust and rapport; and 3) use of local phrases/terms. Adolescents will be fluent in English, yet caregivers may be only speaking Dagbani (local language). Thus, all research assistants (RA) will be fluent in English and Dagbani, and assessments will be available in both languages (using forward/ backward translation by a certified translator). The

in-country Multiple Principal Investigator (MPI) [name] is fluent in Dagbani and will help cross-check the translated documents. The assessments will be conducted by trained RAs in a private location and take approximately 60 minutes with a 10-minute break. Content and construct validity will be conducted for measures to ensure cultural validity where necessary.

Qualitative data collection

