Upon intervention completion, randomly selected 30 dyads from the treatment arm will participate in interviews about their experiences with the ANZANSI intervention. We expect that this sample size will be sufficient in reaching theoretical saturation. Questions will be translated and back-translated by 2 team members fluent in both English and Dagbani (local language). The interviews will be conducted with caregivers and adolescent girls separately in a private place of their choosing by RAs (trained in qualitative interviewing) using pre-established semi-structured interview protocols. The interviews will focus on: 1) Experiences with the intervention and 2) Key multi-level (individual, family, contextual, and program) influences affecting program participation. Semi-structured interviews elicit richer responses⁷⁴ and will help better understand participants' processes and experiences with ANZANSI; potential processes behind key outcomes and mediating variables; and multi-level factors that may have affected their experiences. Interviews will last 1 hour and will be audio-taped. The interviews will assess intervention feasibility and acceptability, not children's psychosocial functioning. Hence, we do not expect the interviews to influence follow-up assessment.

Data analysis

Quantitative data analysis.

Feasibility. We will monitor recruitment rates and staff level of effort, number of screenings conducted, proportion eligible and agreed to enroll. Enrollment of 70% or higher will be considered feasible. We will also record number of rescheduled, cancelled and missed sessions and assessments to inform estimation of staffing needs and retention protocols for future trials.

Acceptability. We will adapt the Client Satisfaction Questionnaire (CSQ) to assess acceptability. Items include: *“How helpful was ANZANSI in addressing school dropout and intention to migrate to urban centers to work?”* and *“How likely are you to recommend ANZANSI to families whose children are at risk of migrating to urban centers to engage in child labor?”* Given the modest sample size, quantitative analyses of intervention data will be largely descriptive and concentrate on tabulating and summarizing satisfaction outcomes.

Preliminary impact. We expect that following intervention, relative to the control arm, participants in ANZANSI will have:

- a. improved school attendance and attitudes toward schooling;
- b. lower mean levels of intentions to migrate;

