- c. improved psychosocial wellbeing, social support and family functioning.

Children will be the units of analysis for the preliminary analyses. We will plot means by group over time to describe overall patterns of change. We will use linear mixed models (LMMs) to evaluate the proposed hypotheses. We will fit LMMs to ensure that all requisite information is available to perform the types of analyses typically undertaken in a formal RCT of intervention efficacy and to obtain valuable effect size information. LMMs will include random intercepts for school membership and random intercepts and slopes for subjects (three-level models).

Additional exploratory analyses will study caregivers and children jointly as the unit of analysis

via dyadic analysis methods such as actor-partner and means-and-deviation models to quantify caregiver vs. child effects and between- vs. within-dyad effects on psychological wellbeing.

Power calculations. Although the study purpose is to determine preliminary feasibility and acceptability rather than conduct formal hypothesis tests, we conducted several power analyses using NCSS PASS to supply additional information. Our power analyses assume $\alpha=.05$, power=.80, 83 participants retained at the final time point following 17% estimated attrition, and a conservative unconditional intra-class correlation coefficient (ICC) of 9.3% based on our previous SUUBI study of school going children and school attendance in Uganda. For the target enrollment proportion of 70% to assess feasibility, the width to the limit of the confidence interval is 24.4% (standardized distance: .28). For continuous standard normal variables to assess acceptability (e.g., CSQ-8), the distance from the mean to the confidence limit is .26. These distances to confidence limits are between small (.20) and medium (.50) effect sizes. For preliminary efficacy exploratory analyses with two post-baseline time points, minimum detectable standardized mean differences ranged from .56 to .69 for within-subjects correlations ranging from .20 to .80. In sum, our study is powered to detect small to medium distances to confidence limits for descriptive statistics and medium to large longitudinal analysis effects depending on the amount of within-subject correlation of responses, though, as noted previously, hypothesis testing is not the study focus.

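### The 24.4% precision quoted for the 70% enrolment target is a full interval width labelled as a distance to the limit, and its stated base is retained girls, not eligible families.

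*Combined protocol and SAP*

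**What the plan says.** Under Data analysis, Feasibility, and again in the footnote to Table 1, the rule is "Enrollment of 70% or higher will be considered feasible". Table 1 lists the related measure as "number of screenings conducted; proportion eligible and agreed to enroll". Neither place says what the proportion is a proportion of.

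Power calculations gives the common assumptions: "83 participants retained at the final time point following 17% estimated attrition", alpha .05 and an intraclass correlation (ICC) of 9.3% taken from school attendance in an earlier Ugandan study. For the 70% target it states that "the width to the limit of the confidence interval is 24.4% (standardized distance: .28". For a standardised continuous acceptability score it gives a distance of .26 from the mean to the limit. It then describes both results as distances to confidence limits lying between a small and a medium effect size.

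Participants fixes enrolment at 100 dyads, 10 per school in ten schools. Study setting places recruitment after the schools have been randomised. Under Recruitment, retention and attrition, schools circulate a flyer and "invite all the caregivers with an eligible child/ren to contact the school for details". In addition, "The study team will organize meetings with families in each of the selected schools to present the study and answer questions". After that, "The research team will then meet with potential participants to engage them in the screening and informed consent process".

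**The concern.** Three things do not fit together.

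- **Label.** A 24.4-point distance from 70% to a limit would be very wide for a study of this size, and it does not agree with the standardised distance of .28 printed beside it.
- **Base.** The section says its calculations assume girls retained at the last visit. Retention to 15 months has no bearing on whether a family agreed to enrol. Every one of the 83 or 100 girls has already enrolled, so on either base the proportion would be 100% by construction.
- **Definition.** With the denominator unstated, the same recruitment log could pass or fail the 70% rule depending on which families are counted.

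Feasibility leads Aim 1, and the feasibility data are meant to inform a later trial. The threshold, and the uncertainty around it, should therefore be readable without guesswork.

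**Working it through.** **Inputs.** Target p = 0.70 (Feasibility); 100 enrolled, 10 schools, 10 per school (Participants); 83 retained, ICC 0.093, alpha .05 (Power calculations). Sidedness is not stated, so a two-sided 95% interval is assumed.

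**Formulas.** Design effect DE = 1 + (m − 1) × ICC, where m is girls or families per school. Effective sample size n_eff = n / DE. The exact interval is Clopper-Pearson at p = 0.70. The standardised distance to the lower limit L is the arcsine difference 2·asin(√0.70) − 2·asin(√L). The distance for a standardised mean is t(.975, n_eff − 1) / √n_eff.

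**Reproducing the printed figures.** Take n = 100 with m = 8.3 (83/10). DE = 1 + 7.3 × 0.093 = 1.679, and n_eff = 100 / 1.679 = 59.6, or 60 rounded. At 60:

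- exact interval 56.8% to 81.2%, full width 24.4 points (printed: 24.4%);
- 13.2 points below 70% and about 11.2 above;
- arcsine distance to the lower limit .275 (printed: .28);
- distance for a mean .258 (printed: .26).

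All three printed figures match, and 24.4% matches as a full width.

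**Testing 24.4 as a true distance.** By the normal approximation it needs n_eff = 0.21 × (1.96 / 0.244)² = 13.5. Its arcsine distance would be .50 to the lower limit (45.6%) or .68 to the upper (94.4%), not .28. Bases of 83 or 100, with or without clustering, give distances to a limit of only about 9 to 15.5 points.

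**Testing the stated base and an eligible-family base** (exact intervals):

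| Base | m | DE | n_eff | Interval | Full width |
|---|---|---|---|---|---|
| 83 retained | 8.3 | 1.679 | 49.4 | 55.3% to 82.2% | 26.9 |
| 100 enrolled | 8.3 | 1.679 | 60 | 56.8% to 81.2% | 24.4 |
| 143 eligible (assumed) | 14.3 | 2.236 | 63.9 | 57.2% to 80.8% | 23.6 |

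The 143 is 100 / 0.70, the number of invited families if 100 enrol at exactly the target. It is not in the documents. For 120 to 200 eligible families, the normal-approximation half-width runs from 11.7 to 10.6 points with clustering.

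**Uniqueness.** The match to 100 enrolled girls does not prove how the figure was made. It mixes a total of 100 with a cluster size of 8.3. A base of about 122 families at 12.2 per school gives DE = 2.042, n_eff = 59.8 and the same 24.4 width. A normal-approximation interval with n = 100 and m = 10 (n_eff 54.4) also has a full width of about 24.4, though it gives .27 for the mean. With 83, the .28 alone can be obtained as 1.96 / √49.4 = .279, but the 24.4 and the .26 cannot. In each case that reproduces 24.4, it is a full width.

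**The case against.** The strongest reply is that little depends on this figure. Power calculations says the analyses only supply additional information and that hypothesis testing is not the focus. No sample size follows from the 24.4%. Correcting the base moves the full width by less than one point (24.4 to 23.6), and correcting the label makes the precision look better than printed, so nobody is falsely reassured. All of that stands, and it limits the weight of the point. It does not make the sentence correct, and it does not supply the missing denominator.

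Two stronger readings are tempting, and the documents support neither.

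- A reader might infer that the 70% is measured only among families who answered the flyer. The flyer route is opt-in, but the section also describes meetings with families in every school, and the denominator is never defined. It may well be limited to families who come forward; the text does not say so.
- A reader might conclude that every eligible girl on the schools' rolls should be the denominator. Enrolment is capped at 10 per school, so that rate would be capped too. With 20 eligible girls per school (an assumption) it could not exceed 50%, however willing the families. Age and absence records would also not settle the other criteria, such as capacity to assent and a caregiver able to consent.

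The plan also lists recruitment rates and the number of screenings alongside the 70% proportion, so it is not the only uptake information collected. It does not say whether the rate will be pooled across arms.

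**Conclusion.** The precision statement is wrong as written. The 24.4% is a full interval width; the distances to the limits are about 13 points below 70% and 11 above. The stated base of 83 does not reproduce it (26.9 points), and neither 83 nor 100 is the denominator of an enrolment proportion. That 100 enrolled girls were used is the best-fitting explanation, not an established fact.

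The effect on precision is small. On the assumed 143 eligible families, an observed 70% would carry an exact interval of about 57% to 81%. This rests on a two-sided 95% interval, on 143 as the count, and on borrowing an ICC for school attendance in Uganda to describe clustering of enrolment in Ghana, which is a further assumption. The more useful gain is a defined denominator for the trial's one numeric feasibility threshold.

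**What to change.** 1. In Power calculations, relabel 24.4% as a full width, or replace it with the two distances to the limits.
2. Recompute it on eligible families approached and drop the reference to retention for this quantity. With about 143 families (stated as an assumption), the exact interval is about 57% to 81%, full width 23.6 points. Say that the ICC is borrowed from a different outcome.
3. In Feasibility and the Table 1 footnote, define the 70% proportion as enrolled dyads divided by families screened eligible and invited before that school's quota of 10 is filled.
4. Report it overall and by arm. Schools are randomised before recruitment and only one arm is offered the savings match, so uptake could differ. By-arm figures are descriptive: half of 63.9 is an effective size of about 32, with a half-width of 1.96 × √(0.21 / 32) ≈ 16 points.
5. If a count of eligible girls who never came forward can be obtained, report it as a separate descriptive reach figure, not as the denominator of the 70% rule.

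The cost is a few sentences of analysis-plan wording and a screening log recording invitations and refusals by school. Design, sample size and intervention are unchanged.

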Treatment arm (ANZANSI). In addition to bolstered care, participants in this arm will receive the ANZANSI intervention described earlier.

Intervention adaptation, delivery, monitoring and fidelity

Community stakeholders will be gathered and engaged in tailoring the content of the existing multiple family group manual focused on child behavioral health used in Ghana. BasicNeeds (implementation partner for the proposed study) staff already trained in this intervention delivery

used for SMART Africa will attend a refresher training before training facilitators to deliver this part of ANZANSI. Ten female facilitators will be selected from the community. Core components of the multiple family group intervention will be maintained. Intervention sessions will occur via 1-hour group meetings facilitated by two facilitators. Adapted protocols will guide the program delivery. Independent observations using rating scales will be made with a random sample of 60% of intervention sessions and used to assess the planned versus actual implementation; evaluate implementation integrity; and examine how strategies were altered to maximize effectiveness and acceptability.

Implementation Process Evaluation

Changes from the planned curriculum will be examined using process notes. Caregivers will report monthly on factors that affect their participation using an implementation checklist that assesses satisfaction and obstacles to program delivery: 1) factors interfering with adolescent girls' or family participation (e.g. insufficient time, health, stigma, competing priorities); 2) concrete obstacles (e.g. weather, transportation, sickness) and 3) site and staffing obstacles (e.g. time & space constraints). Caregivers and adolescent girls will also complete a short checklist on barriers/motivators developed for "Knowledge about the African American Research Experience" (R01MH58566; PI: [name]).

Quantitative Data Collection

Data will be collected at baseline and posttest (9 and 15 months post intervention initiation) from both adolescent girls and their caregivers (see Table 1 for measures).

Table 1. Measures

Variable	Measures
Demographics (A, C)	Demographic survey

School (A, C, S)	1) School Attitude Assessment Survey-Revised 2) School attendance reports
Work Attitudes (C)	Attitudes toward youth employment ⁵⁵
Savings (A, C, B)	1) Bank statements 2) Importance of savings 3) Confidence of savings 4) Financial literacy

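### One acceptability item asks for a single helpfulness rating on two separate targets, school dropout and intention to migrate, so the tabulated answer cannot be assigned to either

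*Combined protocol and SAP*

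**What the plan says.** The Acceptability paragraph under Data analysis says that the CSQ will be adapted and shows two items. The first is "How helpful was ANZANSI in addressing school dropout and intention to migrate to urban centers to work". The second is "How likely are you to recommend ANZANSI to families whose children are at risk of migrating to urban centers to engage in child labor". The analysis is to be mainly descriptive summaries of satisfaction. No companion item and no scoring rule separates the two targets named in the first item.

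Table 1 lists the instrument as "Client satisfaction Questionnaire (CSQ-8; to be adapted"), to be completed by adolescents and caregivers. The same table measures schooling by an attitude survey and school attendance reports. Migration is measured by self-report from girls and caregivers, including "How likely they are to see themselves migrate".

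The hypotheses, stated under Methods and again under Preliminary impact, keep the two apart: (a) concerns school attendance and attitudes toward schooling, and (b) is "lower mean levels of intentions to migrate".

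On timing, Quantitative Data Collection states "Data will be collected at baseline and posttest (9 and 15 months post intervention initiation"), and the text after Table 1 adds "The complete assessment battery is administered at each timepoint". The order of questions within a visit is not given.

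**The concern.** The item is double-barrelled. It asks how helpful the programme was, but for two things at once, and a family may hold different opinions on each. Whatever that family answers, the reader of the table cannot tell which target the answer concerns.

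Acceptability is named beside feasibility in Aim 1(i), and the power section says that feasibility and acceptability, not formal testing, are the purpose of the study. The battery is also meant to inform a later, larger trial. An item on perceived helpfulness should therefore tell the team whether families saw the programme as helping with schooling, with migration, or with both. As worded, it cannot.

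A secondary question is whether the item could influence migration answers. It names intention to migrate as something ANZANSI addresses. Only treatment families can meaningfully answer it, and the same people report their own migration intentions.

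**Working it through.** No arithmetic applies. The plan's only figure for acceptability is the distance of .26 from the mean to the confidence limit. That describes the precision of a score and says nothing about what an item means. The check is a reading of the passages against each other.

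**Step 1: are the two targets distinct in the protocol?** Yes. Schooling is hypothesis (a) and intention to migrate is hypothesis (b), and Table 1 gives them different instruments. The item joins them under one rating.

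**Step 2: can the rating be divided?** Set out the four possible opinions:

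| Helped with schooling | Helped with migration | Accurate answer to the joint item |
|---|---|---|
| Yes | Yes | High |
| No | No | Low |
| Yes | No | None: depends on how the family reads 'and' |
| No | Yes | None: depends on how the family reads 'and' |

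Families in the last two rows may answer for both targets together, for either one, for whichever matters more to them, or at some midpoint. Suppose that in one sample every family is helped only with schooling, and that in another every family is helped only with migration. If families read the question the same way, both samples produce the same table. The two situations call for different conclusions, and the item cannot tell them apart.

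**Step 3: does another element of the plan recover the split?** The Acceptability paragraph gives no separate items and no rule. The outcome measures in Table 1 record attendance, attitudes and intentions. They do not record whether families thought the programme helped with each.

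**Step 4: could the item prime the migration answers?** Under Study arms, "In addition to bolstered care, participants in this arm will receive the ANZANSI intervention", so only those families can rate its helpfulness. Within a visit, priming requires that the CSQ be asked in the same session as the migration questions and before them. The documents state neither. The sentence on the complete battery cannot apply literally to every row of Table 1: nobody can rate ANZANSI at baseline, and the Feasibility row consists of trial records. Across visits, a CSQ given at 9 months comes before the 15-month migration questions whatever the order within a visit. Under Qualitative data collection the plan considers whether questioning could influence follow-up assessment, but only for the interviews, not for the CSQ.

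**The case against.** The strongest reply is that this is one sample item in an unfinished questionnaire, in a pilot whose satisfaction analysis is descriptive. Acceptability also has other sources: interviews with 30 treatment dyads, monthly caregiver checklists that cover satisfaction, a barriers and motivators checklist, and the remaining CSQ items. This stands as an argument that the defect is minor. It does not remove it, because none of these sources, as described, gives a rating of perceived helpfulness for each target. That the instrument is unfinished is a reason to correct the item now.

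Three stronger readings are tempting, and the documents do not support them.

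- A reader might infer that the item biases the migration comparison in favour of treatment. The documents support only that it could push answers. Session and question order are unstated, and treatment families will already know much of the programme's aims after 9 months of sessions on girls' education, gender norms and child labour. The size of any added effect cannot be derived.
- A reader might infer that the joint item hides which component of ANZANSI to keep. The components are family economic empowerment and multiple family groups, whereas dropout and migration are targets. Splitting the item by target would not separate the components.
- A reader might wish to express the defect as a share of the CSQ score or as a range of possible results. The item count and scoring of the adapted form are not fixed, the rating is not described as yes/no, and the documents give no figure for families' opinions.

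**Conclusion.** The point holds as a wording defect in one acceptability item, of minor importance. It follows from the text alone: two targets, one rating, no rule to divide it. It assumes only that the item is used as quoted and that some families see the programme as helping with one target more than the other. No outcome analysis, sample size or trial conclusion is shown to change.

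The possible priming of migration answers is a reason for a costless precaution on question order. It is not a demonstrated bias.

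**What to change.** While the CSQ is being adapted, replace the joint item with two neutrally worded items. One asks how helpful or unhelpful the programme was for keeping the girl in school. The other asks the same about her going to the city to work. Tabulate each separately, for girls and for caregivers.

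Add a line to the interviewer guide placing the CSQ after all outcome scales at each post-baseline visit. This avoids possible priming within a visit. It does not remove carry-over from the 9-month CSQ to the 15-month migration questions, since even the split item must mention the subject. Neutral wording limits that but cannot exclude it.

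The cost is one extra question and one line of instruction. The adapted total would no longer be directly comparable with the standard eight-item score unless the two items are reported apart from it, and the plan should say so. Arms, sample size and analysis models are unaffected.
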